- There was an estimated reduction in time to resolution of the 7 primary influenza symptoms vs placebo of 13% and 17% for the pimodivir 600 mg bid and pimodivir 600 mg bid + OST 75 mg bid treatment groups, respectively, and an estimated increase in time to resolution of the influenza symptoms vs placebo of 7% for the pimodivir 300 mg bid treatment group. The differences in time to resolution compared to placebo treatment were not statistically significant for active treatment groups. However, given that the study was finalized at the interim analysis for early success on virologic response, the sample sizes per arm were relatively small, and clinical outcome comparisons had reduced power to show differences.

In Study 63623872FLZ2002 (hospital study), adult (aged 18 to ≤64 years) and elderly (aged 65 to ≤85 years) hospitalized subjects with influenza A infection received pimodivir 600 mg bid + OST 75 mg bid or pimodivir placebo bid + OST 75 mg bid, for a total of 7 days. The following results were observed:

Viral Kinetics

- The difference (95% CI) in viral titer (by culture) AUC of pimodivir 600 mg bid + OST 75 mg bid treatment vs placebo bid + OST 75 mg bid treatment

was -0.5 (-2.0, 1.0) log₁₀ TCID₅₀/mL*day. For subjects that were treated within 72 hours from onset of symptoms, the difference (95% CI) in AUC was -1.2 (-4.2, 1.8) log₁₀ TCID₅₀/mL*day. For subjects that were treated within 96 hours from onset of symptoms, the difference (95% CI) in AUC was -0.9 (-3.0, 1.3) log₁₀ TCID₅₀/mL*day.

- Based on viral titer (by culture), the median time to viral negativity was 1.1 and 1.3 days for the pimodivir 600 mg bid + OST 75 mg bid and placebo bid + OST 75 mg bid treatment groups, respectively, as estimated from an accelerated failure time model. For subjects that were treated within 72 hours from onset of symptoms, the median time to viral negativity was 1.2 and 1.8 days for the pimodivir 600 mg bid + OST 75 mg bid and placebo bid + OST 75 mg bid treatment groups, respectively, as estimated via the accelerated failure time analysis. For subjects that were treated within 96 hours from onset of symptoms, the median time to viral negativity was 1.2 and 1.6 days for the pimodivir 600 mg bid + OST 75 mg bid and placebo bid + OST 75 mg bid treatment groups, respectively, as estimated via the accelerated failure time analysis.

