11.4. Efficacy Analyses

Descriptive statistics will be used for all efficacy endpoints and will be tabulated by treatment arm and stratification factors (baseline NEWS2, type of baseline SOC, and time since onset of influenza symptoms). Subgroup analyses will be performed by, but might not be limited to, treatment extension, region and age group.

As a confirmatory strategy, to account for multiplicity in the statistical evaluation of the most important efficacy endpoints, a combination of hierarchical testing and the Bonferroni-Holm testing procedure will be applied to control for the overall Type I error rate at the 5% level (2-sided). The following endpoints are included in the confirmatory strategy:

1. Hospital recovery scale at Day 6, ie, primary endpoint
2. Incidence in post-baseline complications
3. Time from start of study drug to hospital discharge
4. Time from ICU admission to ICU discharge
5. Time to return to daily activities
6. Time from start to end of mechanical ventilation
7. Rate of re-hospitalization

First, the primary endpoint will be tested for superiority of pimodivir in combination with SOC over placebo in combination with SOC at the 2-sided 5% significance level. If superiority is shown on the primary endpoint, then the 2 secondary endpoints indicated by 2. and 3. in the sequence above will be tested for superiority using the Bonferroni-Holm testing procedure: the smallest p-value from the analysis of these 2 secondary endpoints will be compared to a significance level of 0.025 and, if statistically significant (ie, 2-sided $p < 0.025$), then the 2-sided p-value for the second endpoint will be compared to a significance level of 0.05. If both endpoints show superiority, the same Bonferroni-Holm testing procedure will be applied to the 2 secondary endpoints indicated by 4. and 5. in the sequence above. If both these endpoints show superiority, the secondary endpoint indicated by 6. in the sequence above will be tested at the 2-sided 5% significance level. If superiority of this sixth endpoint is shown, the seventh and last endpoint in the sequence above will be tested at the 2-sided 5% significance level.

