1.4. Sample Size Justification

The study will enroll 600 subjects between the ages of 13 and 85 years, inclusive. Subjects will be randomized 1:1 to one of the treatment arms.

The sample size is based on the primary endpoint of the hospital recovery scale at Day 6. Based on the proportional odds model and assuming a benefit of approximately 38% reduction of the common odds ratio, a total sample size of 600 subjects (randomized 1:1) is required to obtain a power of 90% [11]. Inclusion of stratification factors would provide some improvement on the derived power.

In the sample size calculation it is assumed that the distribution of subjects treated with placebo in combination with SOC treatment will be as follows on Day 6:

- Not hospitalized: 30%
- Non-ICU hospitalization, not requiring supplemental oxygen: 30%
- Non-ICU hospitalization, requiring supplemental oxygen: 25%
- Admitted to the ICU, not requiring invasive mechanical ventilation: 5%
- Requiring invasive mechanical ventilation: 5%
- Death: 5%

This sample size is robust to mild to moderate changes in this distribution.

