4.1. Demographics and Baseline Characteristics

Demographics and baseline disease characteristics will also be done on the PP and ITT-ni sets.

Descriptive statistics or frequency tabulation will be provided for the following parameters.

- Demographic parameters:
 - Sex (Male, Female)
 - Race (White, Black or African American, Asian, American Indian or Alaska Native, Native Hawaiian or Other Pacific Islander, Multiple). The specification of the category ‘Multiple’ will only be listed. The ‘Not reported category’ will not be added for the denominator.
 - Ethnicity (Hispanic or Latino, Not Hispanic or Latino)
 - Country
 - Geographic region (Based on country according to UN classification of Geographic regions^[9]: Europe/Africa, Northern-America, Latin America and the Caribbean, Asia and Oceania)
 - Age (years and categories: 13-17 years [≥ 13 - < 18], 18-65 years [≥ 18 - ≤ 65], 66-85 years [> 65 - ≤ 85])
 - Age (years and categories: Adolescents (12-17 years) [≥ 12 - ≤ 17], Adults (18-64 years) [≥ 18 - ≤ 64], From 65 to 84 years [≥ 65 - ≤ 84], 85 years and over [≥ 85])
 - Weight at baseline (kg)
 - Height at baseline (cm)
 - BMI at baseline = Weight at baseline (kg) / (Height at baseline (m))² (rounded to 1 decimal. Although available in the raw data, BMI will be recalculated from last weight and height measurement before start of treatment)
 - Current Tobacco use: tobacco, cigarettes, cigars, patches/gum, pipes, E-cigarettes or equivalent, smokeless tobacco (Yes, No, Missing). Note that ‘No’ also includes ex-smokers.
 - Childbearing potential (only listed)

- Baseline disease characteristics:
 - Influenza A subtype category (A/H1N1, A/H3N2, No subtype)
 - Baseline influenza A viral load (\log_{10} vp/mL), assessed by qRT-PCR
 - Baseline influenza A viral titer (\log_{10} TCID₅₀/mL) assessed by viral culture

- qRT-PCR negativity at baseline
- Viral culture negativity at baseline
- Broad respiratory panel (show the reported pathogen)
- Return to daily activities at baseline
- Patient Global Impression of Severity of Influenza symptoms at baseline
- EQ-5D VAS at baseline
- EQ-5D Valuation index at baseline
- NEW2 Score at screening (4-5, ≥ 6), as randomized
- NEW2 Score at screening (4-5, ≥ 6), actual
- Hospital recovery scale category at baseline
- Fundamental hospital recovery scale category at baseline
- Respiration rate at baseline (breaths/min)
- Arterial oxygen saturation at baseline on room air (%)

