
Viral titer AUC_{0-10d} trapezoidal method
	
Viral titer AUC calculated from baseline to Day 10:
 
AUC is calculated by the trapezoidal summation rule, based on planned days of, including the timepoints with (imputed) values available:
 $\text{Sum over } i \text{ of } (t_{i+1}-t_i) * (\text{Viral titer}_{i+1} + \text{Viral titer}_i) / 2$ 
The following rules will be applied in the order described below to deal with missing values before calculating the Viral titer AUC:
 
 • If the baseline value is missing, then the mean baseline value over all subjects in the ITT-i set will be used. • If a single or sequential intermediate value (not the baseline value) is missing, then the missing value will be replaced by linear interpolation of the two adjacent values. Note: this is done automatically when applying the trapezoidal summation rule. If Day 10 value is missing, but there is an assessment after Day 10, then this value will be used to interpolate the value of Day 10. • If the Day 10 value is missing, and there are no values available after Day 10, then it will be imputed with the last observed post-baseline value (LOCF). 
Note: In case no post baseline value is available the AUC will be missing.

Time to viral negativity by qRT-PCR (days) [Time-to event]
	
The time to viral negativity is defined as the time (in days) from first study drug intake until a subject is considered influenza A viral negative. This is the first timepoint of two consecutive timepoints with a negative nasal MT swab, i.e. the first and next assessment equal to 'negative' (ignoring missing values). In case the first 'negative' is the last available assessment the subject is considered to have reached viral negativity at this last assessment.
 
If this doesn't occur, a subject will be censored at the time of the last observed non-negative swab + 1 day. Note that for deriving the time to viral negativity by qRT-PCR every subject is considered positive at baseline. For subjects without postbaseline records, they are censored at Day 1.

Time to viral negativity by viral culture (days) [Time-to event]
	
The algorithm for Time to viral negativity by viral titer is similar as 'Time to viral negativity by viral load' but viral titer assessments are used instead.

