5.3.2.1. Clinical outcome

Time-to event parameters for clinical outcome

The time-to event parameters for clinical outcome will be analyzed as described above using a stratified Gehan-Wilcoxon test, a stratified log-rank test, a Kaplan-Meier analysis, an accelerated failure time model and a Cox proportional hazards model. The Gehan-Wilcoxon test is the primary analysis for time-to-event parameters. The Kaplan-Meier analysis will provide the primary estimation of time-to-event.

Duration parameters

Descriptive statistics of the duration parameters will be shown for all subjects that had the specific event. e.g. only subjects admitted to ICU will be included in the total time in ICU analysis.

Total length of hospitalization, total time in ICU, total duration of antibiotics, and total time on mechanical ventilation will be analyzed by using the Hodges-Lehman approach. Corresponding 95% CIs will be presented as well.

Incidence parameters

For each parameter the number and percentage of subjects in each category and subcategory will be tabulated and listed. All Subjects in the applicable analysis set will be counted for the denominator of the proportion.

The occurrence (yes/no) as described for the incidence parameters will be analyzed using logistic regression as described above (Section 5.3.2).

The occurrence (yes/no) of influenza complications will be analyzed using logistic regression as described above for the following categories:

- the overall influenza complications
- the pulmonary complications,
- the extrapulmonary complications
- the infectious complications
- the non-infectious complications
- the major complications
- the minor complications
- the pulmonary complications including sinusitis and otitis

Hospital recovery scale outcome and fundamental hospital recovery scale outcome on Day 2 to 14

This parameter will be analyzed analogous to the primary endpoint: hospital recovery scale outcome on Day 6, but then for Day 2 to 14 with Day 6 excluded for the HRS and including Day 6 for the fundamental HRS. The proportional odds model will be applied, and the proportional odds assumption will be tested for the treatment effect. The same 5 dichotomization of the HRS will be analyzed using a logistic regression model. Also, similarly as the primary endpoint the Van Elteren test will be provided in case the proportional odds assumption is not valid. The MI analysis will not be applied.

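### Time to viral negativity by culture has no rule for subjects already culture-negative at baseline, which dilutes the Gehan-Wilcoxon comparison and stops the median being a clearance time

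*SAP*

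**What the plan says.** SAP 2.2.2.1 admits a treated subject to ITT-i on central PCR or, in defined cases, a local test. A positive culture is not required. SAP 5.3.1.2 calls a titer negative when it is below LOQ. SAP 4.1 lists "Viral culture negativity at baseline" among the baseline characteristics, so such subjects are foreseen, but no share is given.

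For qRT-PCR, time runs from first drug intake to the first of two consecutive negative swabs, ignoring missing ones. A first negative that is also the last available swab counts as the event. The SAP adds that "for deriving the time to viral negativity by qRT-PCR every subject is considered positive at baseline". The culture entry says only: "The algorithm for Time to viral negativity by viral titer is similar as" the PCR one, with titers substituted.

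SAP 5.3.2.2 analyses both versions like the clinical time-to-event endpoints, for which SAP 5.3.2.1 states: "The Gehan-Wilcoxon test is the primary analysis for time-to-event parameters". Its strata are type of baseline SOC, time since symptom onset and NEWS2. Baseline titer enters the AFT and Cox models only.

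Time to viral negativity is a superiority objective by both assays (Protocol 2.1.1, SAP 1.1). It is not among the seven endpoints of the confirmatory strategy (Protocol 11.4, SAP 5.1.1).

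**The concern.** Take a subject who is below LOQ before dosing and on the Day 2 and Day 3 swabs. With no exclusion, this subject reaches negativity at Day 2 whichever arm they are in. There was no change from positive to negative, so the event says nothing about the drug.

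Such events tie at the earliest time point, where a Gehan-Wilcoxon test puts its greatest weight. They pull the arms together, and any chance imbalance in baseline status adds noise. If half or more of the subjects were of this kind, the overall median would simply be the time of the first swab.

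The population makes such subjects plausible. Entry is allowed up to 96 hours after onset and after up to three doses of an influenza antiviral. Protocol 1.1 reports for the Phase 2b hospital study that "the median time to viral negativity was 1.1 and 1.3 days for the pimodivir 600 mg bid + OST 75 mg bid" and placebo arms respectively, which is about when the Day 2 swab falls.

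**Working it through.** **The plan's own figure.** SAP 1.4 says "a total sample size of 600 subjects (randomized 1:1) is required to obtain a power of 90" percent, "assuming a benefit of approximately 38% reduction of the common odds ratio", for the primary endpoint. With OR = 0.62 and a placebo distribution of 30/30/25/5/5/5%, Whitehead's formula is

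N = 12(z₀.₉₇₅ + z₀.₉₀)² / [(ln OR)²(1 − Σp̄³)] = 12 × 10.507 / (0.2285 × 0.9175) = 601.

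Power at N = 600 is 89.9%, so the stated figure reproduces. No figure is stated for the culture endpoint, so what follows rests on assumptions.

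**Inputs from the documents.** 300 per arm; in-hospital swabs on Days 2, 3, 4, 5, 8, 10 and 14; Phase 2b hospital culture medians of 1.2 vs 1.6 days for subjects treated within 96 hours (Protocol 1.1).

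**Assumptions.** A share f is culture-negative at baseline and has its event at the Day 2 swab in both arms. Tests are unstratified, two-sided 5%. Three clearance models apply to culture-positive subjects:

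- A: lognormal, control median 3 days (not in the documents), log SD 0.8, pimodivir 18% shorter. The 18% is the Phase 2b community-study figure for 600 mg monotherapy, where the assay is not named.
- B: Weibull shape 1.0, medians 1.2 vs 1.6 days.
- C: lognormal, log SD 0.8, medians 1.2 vs 1.6 days.

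Power (%) with baseline-negatives included → excluded, and points lost:

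| f | A | B | C |
|---|---|---|---|
| 10% | 70 → 79 (9) | 77.3 → 82.1 (4.8) | 95 → 97 (2) |
| 20% | 53 → 74 (21) | 64.2 → 76.5 (12.3) | 87 → 95 (8) |
| 40% | 23 → 59 (36) | 41.4 → 66.0 (24.6) | 64 → 87 (23) |
| 60% | 13 → 46 (33) | 22.6 → 47.7 (25.1) | 35 → 72 (37) |

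Repeat runs of A at f = 40% gave 28 → 61 and 26 → 63, so single entries are uncertain by a few points.

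**Share of attainable power lost.** A: 1 − 53/74 = 28% at f = 20% and 1 − 23/59 = 61% at f = 40%. B: 1 − 31.1/56.6 = 45% at f = 50% and 1 − 22.6/47.7 = 53% at f = 60%. C: 1 − 64/87 = 26% at f = 40% and 1 − 35/72 = 51% at f = 60%.

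**Analytic worst case.** Suppose no positive subject clears by the first swab. The treatment contrast in a rank test then shrinks by (1 − f)² and the tie-corrected variance by (1 − f³), so

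z(included)/z(excluded) = (1 − f)^1.5 / √(1 − f³).

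If exclusion gives 90% power, inclusion gives 79% at f = 10%, 64% at 20%, 49% at 30% and 34% at 40%. At f = 20%, for example, the ratio is 0.718, and 0.718 × 3.24 − 1.96 = 0.37, which is 64%.

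**Milder cases.** With medians 1.2 vs 1.8 days (treated within 72 hours) and Weibull shape 1.5, the loss is under 1 point at f = 20% and 8 points at 40% (91.7 → 99.8). With the overall medians of 1.1 vs 1.3 days and shape 1.0, it is 12 points at 40%, where only 29.3% is attainable. The log-rank test loses less: under B at f = 40%, 64.8 → 75.4.

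**The case against.** A reader might infer that the rule removes most of the power. The documents do not support that. They give no baseline-negative share, and more than half of the attainable power goes only at about 40% (A and the analytic worst case) to 60% (B and C). Model A also places true clearances well after the Day 2 swab, which favours the concern. Models B and C use medians from the documents, but those may already include baseline-negative subjects; Protocol 1.1 does not say.

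A reader might also infer that every baseline-negative subject becomes an event at the first swab regardless of drug. The two-consecutive-negatives rule prevents that for anyone positive on either of the first two swabs, and one titer below LOQ does not prove that shedding has stopped. If 30% of baseline-negatives (an assumption) in fact cleared like the rest, one run of A with included powers of 55, 26 and 12% at f = 20, 40 and 60% would give 60, 40 and 26%.

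Three further points stand. The note treating everyone as positive at baseline is written for qRT-PCR, so carrying it over to culture is an inference; if it does not carry over, the handling is undefined, and a sentence is needed either way. The AFT and Cox models adjust for baseline titer, and titer over time is modelled separately with its baseline as covariate. No confirmatory claim depends on this endpoint.

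None of this supplies the missing rule or protects the test named as primary.

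**Conclusion.** The gap is real and its direction is clear: including subjects who were never culture-positive dilutes the Gehan-Wilcoxon comparison, and the resulting median cannot be read as a clearance time. Its size is conditional. Across models A to C the cost is roughly 2 to 10 points of power at a 10% baseline-negative share, 8 to 21 at 20% and 23 to 36 at 40%. It is smaller where the effect is large enough to keep power near its ceiling and larger in the analytic worst case. These figures rest on assumed clearance distributions, the in-hospital swab grid, unstratified tests and baseline-negatives who stay negative. The consequence is a weakened and hard-to-interpret secondary superiority analysis, not a threat to the primary or confirmatory results.

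**What to change.** In SAP 5.3.1.2 and 5.3.2.2:

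- Base the main analysis of time to viral negativity by culture on ITT-i subjects with a quantifiable baseline titer. Alternatively, keep ITT-i and add baseline culture status as a stratum in the Gehan-Wilcoxon test. For the test the two are equivalent when all baseline-negatives tie at the first swab, because their stratum then contributes nothing. Stratifying does not repair the median, so the Kaplan-Meier estimate should still be shown for culture-positive subjects.
- State how missing baseline culture is handled.
- Report the number baseline-negative and the number missing by arm.
- Keep the all-ITT-i version as supportive.

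The cost is a few sentences and no new data, since baseline culture is already collected and tabulated. The baseline swab is scheduled before the first dose, so restricting on it preserves the randomised comparison. The downside is fewer informative subjects in this one analysis and, under restriction, a population narrower than the ITT-i set named for efficacy in Protocol 11.1 and SAP 2.2.2.

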5.3.1.3. Patient Reported Outcomes

Measurement	Formula
Daily activities resumption	
The daily activities resumption will be assessed once daily by means of the question 'Over the past 24 hours, how much has influenza interfered with your ability to carry out your daily activities?'
 
The responses will be dichotomized: 'Not at all' and 'A little bit' will be considered as category “returned to daily activities” and responses 'Somewhat', 'Quite a Bit' and 'Very much' will be considered in category “not returned to daily activities”.

Time to return to daily activities (days) [Time-to event]	
The time to return to daily activities is defined as the time in days from initiation of study treatment (baseline assessment excluded) to the first of a successive series of 2 recordings in which the response is considered as returned to daily activities. The 2 successive recordings may have been done over 3 scheduled successive analysis timepoints, in case of 1 missing in between timepoint.
 
In case the return to daily activities is not achieved, data will be censored.
 
Censoring will be done as follows:
 
 1) Last non-missing record in indicate return to daily activities (but insufficient recordings) Censoring will be done at the first record of return to daily activities 2) Last non-missing record does not indicate return to daily activities Censoring will be done one day (24 hours) after the last observation. 
The time to return to daily activities is calculated as: Date and time of event (actual) or censoring - date and time of first dose of study drug)/(3600*24), rounded to one decimal.
 
Subjects without postbaseline records are excluded from the analysis.

Patient Global Impression of Severity of Influenza symptoms	
The PGIS captures daily influenza symptom severity from the subjects’ perspective per timepoint. Responses will be categorized as :“No Flu symptoms today”, and “Mild”, "Moderate", "Severe" or “Very Severe”.


Patient global Impression of Change in Influenza symptoms
	
The PGIC^[4] is aimed to capture the subject’s perceptions of improvement or deterioration in the severity of influenza symptoms compared to when the subject arrived to the hospital for influenza treatment and this is done per timepoint.^[5]
 
Categories are: “Much better”, “Somewhat better”, “A little better” “About the same”, “A little worse”, “Somewhat worse” and “Much worse”.
																																																																																	

EQ-5D dimension parameters: Mobility, Self-care, Usual activities, Pain/discomfort, Anxiety/depression
	
The EQ-5D (Attachment 5)^[2] descriptive system consists of 5 dimensions (mobility, self-care, usual activities, pain/discomfort, anxiety/depression) with 5 possible levels (no problems (level code = 1), slight problems (level code = 2), moderate problems (level code = 3), severe problems (level code = 4), extreme problems (level code = 5)) (see Table 5). Each dimension will be captured in one parameter
 
Table 5: EQ-5D Dimensions
 
  
 Dimension	Level	Interpretation	
   
 1	Mobility	1	No problems	I have no problems in walking about	
 
 2	Slight problems	I have slight problems in walking about	
 
 3	Moderate problems	I have moderate problems in walking about	
 
 4	Severe problems	I have severe problems in walking about	
 
 5	Extreme problems	I am unable to walk about	
 
 2	Self-care	1	No problems	I have no problems washing or dressing myself	
 
 2	Slight problems	I have slight problems washing or dressing myself	
 
 3	Moderate problems	I have moderate problems washing or dressing myself	
 
 4	Severe problems	I have severe problems washing or dressing myself	
 
 5	Extreme problems	I am unable to wash or dress myself	
 
 3	Usual activities	1	No problems	I have no problems doing my usual activities	
 
 2	Slight problems	I have slight problems doing my usual activities	
 
 3	Moderate problems	I have moderate problems doing my usual activities	
 
 4	Severe problems	I have severe problems doing my usual activities	
 
 5	Extreme problems	I am unable to do my usual activities	
 
 4	Pain/discomfort	1	No problems	I have no pain or discomfort	
 
 2	Slight problems	I have slight pain or discomfort	
 
 3	Moderate problems	I have moderate pain or discomfort	
 
 4	Severe problems	I have severe pain or discomfort	
 
 5	Extreme problems	I have extreme pain or discomfort	
 
 5	Anxiety/depression	1	No problems	I am not anxious or depressed	
 
 2	Slight problems	I am slightly anxious or depressed	
  
	Dimension		Level		Interpretation	1	Mobility	1	No problems	I have no problems in walking about	2	Slight problems	I have slight problems in walking about	3	Moderate problems	I have moderate problems in walking about	4	Severe problems	I have severe problems in walking about	5	Extreme problems	I am unable to walk about	2	Self-care	1	No problems	I have no problems washing or dressing myself	2	Slight problems	I have slight problems washing or dressing myself	3	Moderate problems	I have moderate problems washing or dressing myself	4	Severe problems	I have severe problems washing or dressing myself	5	Extreme problems	I am unable to wash or dress myself	3	Usual activities	1	No problems	I have no problems doing my usual activities	2	Slight problems	I have slight problems doing my usual activities	3	Moderate problems	I have moderate problems doing my usual activities	4	Severe problems	I have severe problems doing my usual activities	5	Extreme problems	I am unable to do my usual activities	4	Pain/discomfort	1	No problems	I have no pain or discomfort	2	Slight problems	I have slight pain or discomfort	3	Moderate problems	I have moderate pain or discomfort	4	Severe problems	I have severe pain or discomfort	5	Extreme problems	I have extreme pain or discomfort	5	Anxiety/depression	1	No problems	I am not anxious or depressed	2	Slight problems	I am slightly anxious or depressed
Dimension		Level		Interpretation																																																																														
1	Mobility	1	No problems	I have no problems in walking about																																																																														
		2	Slight problems	I have slight problems in walking about																																																																														
		3	Moderate problems	I have moderate problems in walking about																																																																														
		4	Severe problems	I have severe problems in walking about																																																																														
		5	Extreme problems	I am unable to walk about																																																																														
2	Self-care	1	No problems	I have no problems washing or dressing myself																																																																														
		2	Slight problems	I have slight problems washing or dressing myself																																																																														
		3	Moderate problems	I have moderate problems washing or dressing myself																																																																														
		4	Severe problems	I have severe problems washing or dressing myself																																																																														
		5	Extreme problems	I am unable to wash or dress myself																																																																														
3	Usual activities	1	No problems	I have no problems doing my usual activities																																																																														
		2	Slight problems	I have slight problems doing my usual activities																																																																														
		3	Moderate problems	I have moderate problems doing my usual activities																																																																														
		4	Severe problems	I have severe problems doing my usual activities																																																																														
		5	Extreme problems	I am unable to do my usual activities																																																																														
4	Pain/discomfort	1	No problems	I have no pain or discomfort																																																																														
		2	Slight problems	I have slight pain or discomfort																																																																														
		3	Moderate problems	I have moderate pain or discomfort																																																																														
		4	Severe problems	I have severe pain or discomfort																																																																														
		5	Extreme problems	I have extreme pain or discomfort																																																																														
5	Anxiety/depression	1	No problems	I am not anxious or depressed																																																																														
		2	Slight problems	I am slightly anxious or depressed																																																																														

	
 
 		3	Moderate problems	I am moderately anxious or depressed	
 
 		4	Severe problems	I am severely anxious or depressed	
 
 		5	Extreme problems	I am extremely anxious or depressed	
 
			3	Moderate problems	I am moderately anxious or depressed			4	Severe problems	I am severely anxious or depressed			5	Extreme problems	I am extremely anxious or depressed
		3	Moderate problems	I am moderately anxious or depressed												
		4	Severe problems	I am severely anxious or depressed												
		5	Extreme problems	I am extremely anxious or depressed												
EQ-5D visual analogue scale (VAS)	EQ-5D VAS is a continuous score ranging from 0 (worst health you can imagine) to 100 (best health you can imagine).															
EQ-5D VAS change from baseline	EQ-5D VAS post-baseline value – EQ-5D VAS baseline value															
EQ-5D VAS clinically relevant change from baseline	The change from baseline in EQ-5D VAS will be categorized in two ways: 
 1. $\leq -7, -6$ to $6, \geq 7$ 2. $\leq -10, -9$ to $9, \geq 10$ 															
EQ-5D Valuation index	EQ-5D Valuation index summarizes the information of the 5 dimensions of the descriptive system. 
 a. Assign the level code 1, 2, 3, 4 and 5 to each level of the 5 dimensions (see table) b. Create a health state for each patient-time point combination. A health state is a combination of 5 level codes; one level code for each dimension. The dimensions are ordered as described in the table above. E.g. health state 12543 indicates ‘no problems in walking about, slight problems washing or dressing myself, unable to do my usual activities, severe pain or discomfort, moderately anxious or depressed’. c. Assign an index value to each health state as defined in Attachment 5 where EQ-5D health state is converted to a single summary index by applying a formula that essentially attaches weights to each of the levels in each dimension. The algorithm is based on the valuation of EQ-5D health states using the UK TTO (=time trade-off method) based value set. 															
EQ-5D Valuation index change from baseline	EQ-5D valuation index post-baseline value – EQ-5D valuation index baseline value															

